### 7.4 Cross Over Between Trial Treatments/Additional Treatments

The NERVES trial protocol will only allocate **initial treatment** for sciatica, either TFESI or microdiscectomy. During the course of follow up participants may require further intervention for sciatica as per routine NHS practice. Further clinical intervention is permitted for trial participants without the patient having to withdraw from the trial.

If a patient receives additional treatment information on the type of intervention (e.g., TFESI or surgery), the details of the treatment received and the reason will be collected and the patient should stay in the trial.

Trial participants are able to crossover prior to receiving their initial treatment allocation **without withdrawing from the trial** e.g., if they become unsuitable for the treatment they are initially randomised to. This should be recorded on the treatment CRF with the reason for crossover indicated.

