**Table 3: Trial Assessments**

Procedures	Screening / Baseline (T = 0)	Follow-Up Schedule					Unscheduled visits 
		Intervention T=6 weeks 	Time Point T = 18 weeks	Timepoint T = 30 weeks 	Timepoint T = 42 weeks 	Timepoint T = 54 weeks	
Signed Consent Form	X 						
Assessment and Confirmation of Eligibility Criteria	X 						
Review of Medical History	X 						
Review of Concomitant Medications	X 	X	X			X	
Oswestry Disability Questionnaire	X 		X	X 	X 	X	
Health Economic Assessment	X 	X	X	X 	X 	X	
EQ-5D-5L	X 		X	X 	X 	X	
Numerical rating score for leg and back pain	X 		X	X 	X 	X	
Modified Roland-Morris outcome score for sciatica	X 		X	X 	X 	X	
Core Outcome Measures Index (COMI)	X 		X	X 	X 	X	
Study Intervention		X					
Pregnancy Assessment	X	X	X			X	X
Physical Examination	X 		X			X	
Treatment satisfaction (Likert scale)			X	X	X	X	
Return to work			X			X	
Assessment of Related Adverse Events		X	X			X	X
Assessment of additional interventions given to the participant during the trial period			X			X	X 
Telephone follow up of non-responders				(X) 	(X) 		

(X) – As indicated/appropriate.

 Completed prior to randomisation

 Treatment is expected to occur within 6 weeks of randomisation and no later than 12

 Patient is not required to attend clinic at 30 and 42 weeks; Questionnaire posted to the participant by the trial site and posted back to the CTTC by the patient

 Telephone follow up will typically follow one week after initial issue of questionnaire

 Additional visits for further treatment (e.g. TFESI or surgery) may occur as part of routine practice

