## 9.5 Interim Monitoring and Analyses

### 9.5.1 Internal Pilot

After the internal pilot, if all of the following criteria are met, then the trial will progress to the main phase.

- (1) At least 30 patients have been recruited at the end of the internal pilot study.  
If fewer than 30 patients are recruited, then ways to improve recruitment will be considered, e.g. increasing number of centres, improving consent process to increase patient understanding and willingness to be randomised, widening eligibility based on new evidence.
- (2) The consent rate is 40% or more.  
If the consent rate is less than 40%, information collected on the reasons for non-consent will be considered to identify any aspects amenable to change. If declining consent is predominantly due to patients favouring one treatment over the other, based on full understanding, then the decision may be made to abandon plans for the full trial.
- (3) Fewer than 10% of patients are unhappy with their allocation, and receive the alternative treatment instead.  
If more than 20% of patients are unhappy with their allocation, and receive the alternative treatment instead, consideration will be given to not pursuing the main trial. If the number is between 10% and 20%, the consent process at each centre will be explored to ensure that patients have full understanding.
- (4) Fewer than 50% of patients in the injection group proceed to surgery.  
If more than 50% proceed to surgery, given that this is a pragmatic trial and that meaningful data may still be derived from the results, the TSC/IDSMC will evaluate the reasons behind

crossover and consider stopping the trial if there is a genuine difference in the two treatment efficacies.

Any plans to revise the trial based on these analyses will be submitted to the IDSMC and TSC prior to discussions with the trial funder.

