### 8.3. Treatment compliance

Compliance with the randomised study intervention will be monitored by the CTRC through completion of case report forms at site recording the intervention given and the allocation provided by the online randomisation system. Any deviations from the randomised intervention will be explored with site.

During the follow-up patients may require further clinical intervention, which is permitted without the patient having to withdraw. Details of the treatment received and the reason for treatment will be collected. If patients crossover prior to receiving their initial treatment allocation then this should be recorded, with a reason, on the CRF "Form 3: Treatment Form".

The number of patients who start on either treatment (arm A or B) and go on to receive the alternative treatment should be reported in a way that shows:

- The number of patients who started on TFESI and switched to surgical microdiscectomy
- The number of patients who started on surgical microdiscectomy and switched to TFESI
- The number of patients who were allocated to and received TFESI only
- The number of patients who were allocated to and received surgical microdiscectomy only
- The number of injections received by i) patients on the TFESI treatment only, and ii) patients receiving surgery and TFESI

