## 17. **Efficacy Evaluations**

### 17.1. **Data Sets Analysed**

The principle of intention-to-treat, as far as practically possible, will be the main strategy of the analysis adopted for the primary outcome and all the secondary outcomes. These analyses will be conducted on all randomised participants, in the group to which they were allocated, and for whom the outcome(s) of interest have been observed/measured.

The membership of the analysis set for each outcome will be determined and documented and reasons for participant exclusion will be given.

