## 18 Missing data and withdrawals

The numbers (with reasons) of losses to follow-up and withdrawals over the course of the trial will be summarised by treatment arm. The primary outcome is ODQ score at 18 weeks post-randomisation so if a patient withdraws after 18 weeks they will still contribute towards the primary analysis, given that consent to use all existing data collected up to that point is not removed.

The number of patients with missing data for the primary outcome and each secondary outcome will be presented in a table along with percentages.

Sensitivity analyses will be carried out if the amount of missing data is greater than 10%. Multiple imputation will be used to assess the robustness of the analysis to missing primary outcome data. The multiple imputation method will follow the guidelines set out in Jakobsen et al [14]. PROC MI in SAS will be used to generate 50 complete data sets. The imputation model will include all variables included in the primary outcome analysis model (treatment group, centre and baseline ODQ), and also ODQ measured at additional time points. The random seed for the imputation process will be pre-specified as 753. The complete data sets will be analysed using the model specified in section 17.4.1.2, and the results of all models combined using PROC MIANALYZE. The overall summary adjusted mean difference will be presented with 95% confidence intervals, to assess the sensitivity of the primary analysis to missing data.

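### The imputation model for a missing week-18 ODQ uses later ODQ scores but no term for surgery in between, so it would miss bias if missed week-18 scores go with later surgery

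*SAP*

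**What the plan says.** The primary analysis is a linear regression of week-18 ODQ on treatment, centre and baseline ODQ (SAP 17.4.1.2). It is run on participants "in the group to which they were allocated, and for whom the outcome(s) of interest have been observed/measured" (SAP 17.1). A questionnaire outside 18 ± 6 weeks, or with fewer than 8 of 10 items answered, is excluded (SAP 17.4.1.1), so it also counts as missing.

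SAP 18 makes the check on missing data conditional: "Sensitivity analyses will be carried out if the amount of missing data is greater than 10" per cent. The check is multiple imputation with 50 data sets, and the variables named for the imputation model are "treatment group, centre and baseline ODQ), and also ODQ measured at additional time points". Nothing about further treatment is named.

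Protocol 7.4 expects that "During the course of follow up participants may require further intervention for sciatica as per routine NHS practice", and adds that "Further clinical intervention is permitted for trial participants without the patient having to withdraw from the trial". The information is collected: Protocol Table 3 lists "Assessment of additional interventions given to the participant during the trial period" at weeks 18 and 54 and at unscheduled visits, and Table 1 assigns Form 8 to the same visits. In the SAP it is used only for counts, such as "The number of patients who started on TFESI and switched to surgical microdiscectomy" (SAP 8.3).

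**The concern.** An ODQ at week 30, 42 or 54 means different things with and without an operation since week 18. Without one, a low later score suggests a low week-18 score. With one, a low later score is compatible with a high week-18 score, because a poor result at that point is a plausible reason for the operation. The named imputation model fits a single relation to both kinds of patient, so it places surgery-bound patients too low at week 18.

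That matters if such patients are over- or under-represented among those with a missing week-18 score. Observed and missing patients then differ on something related to the outcome that the model cannot see, and the imputed analysis stays close to the complete-case one for the wrong reason. A reader would take the agreement as reassurance.

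**Working it through.** **The plan's own figures.** The documents give no figure for the imputation. The sample-size inputs used below reproduce: 172/2 = 86 per group; 86 × (1 − 0.49²) = 86 × 0.7599 = 65.4, rounded up to 66; 66/0.9 = 73.3, rounded up to 74 per group, 148 in total (Protocol 9.4, 9.4.2). With 66 per group, the standard error of the adjusted difference is 20 × √0.7599 × √(2/66) = 3.03 points.

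**Inputs.** From the documents: SD 20, target difference 10, baseline to follow-up correlation r = 0.49. Assumed, because the documents give none: 10%, 30% or 50% of the injection arm operated on after week 18, more often those with a high week-18 ODQ; a 15- or 25-point fall in later ODQ after surgery; correlation 0.7 between successive follow-up scores; 10% or 20% of week-18 scores missing; week-18 means of 30 (surgery) and 35 (injection).

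**Step 1: what is imputed.** In large-sample simulation (400,000 per scenario), injection patients with a missing week 18 and later surgery had true means of about 45 to 61. The named model gave about 36 to 47, which is 6 to 19 points too low. The injection-arm average was 35, and injection patients without later surgery averaged 24 to 33.

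**Step 2: size of the complete-case bias by hand.** Let π be the share of the injection arm going to later surgery, π_obs that share among those with week 18 observed, and Δ the gap in week-18 mean between the two kinds of patient. Baseline adjustment takes back a fraction r² of the imbalance, so

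bias ≈ (π_obs − π) × Δ × (1 − r²).

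- Surgery-bound patients twice as likely to be missing, 10% missing, π = 0.30: missing 15.4% v 7.7%; π_obs = 0.30 × 0.846/0.90 = 0.282; Δ = 50.3 − 28.4 = 21.9; bias = −0.018 × 21.9 × 0.76 = −0.30. Simulated: −0.30.
- Four times as likely, 20% missing, π = 0.30: missing 42.1% v 10.5%; π_obs = 0.30 × 0.579/0.80 = 0.217; Δ = 50.4 − 28.4 = 22.0; bias = −0.083 × 22.0 × 0.76 = −1.39. Simulated: −1.39.
- Surgery-bound patients missing less often (5% v 13%), π = 0.30, same Δ: π_obs = 0.285/0.894 = 0.319; bias = +0.019 × 22.0 × 0.76 = +0.3.

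**Step 3: does the planned imputation remove it?** Bias in the treatment difference in ODQ points (negative favours injection), over the assumed grid:

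| Week-18 missingness | Complete case | Planned MI | MI plus dated surgery indicators |
|---|---|---|---|
| Completely at random | about 0 | about 0 | about 0 |
| Depends on baseline ODQ only | about 0 | at most 0.1 in size | at most 0.2 in size |
| Surgery-bound 2 times as likely | −0.2 to −0.7 | −0.1 to −0.7 | about 0 |
| Surgery-bound 4 times as likely | −0.4 to −1.4 | −0.4 to −1.4 | about 0 |
| Depends on week-18 ODQ itself (ratio 3) | −0.7 to −1.6 | −0.4 to −1.1 | −0.3 to −0.8 |

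**Step 4: other settings.** With a true difference near 9, 30% later surgery and week 18 missing in 30% of those patients v 10% of others, a large-sample run gave full data 9.0, complete case 8.1, planned MI 8.0, MI plus a surgery indicator 9.0. Equal missingness gave 9.0 v 9.0. With surgery-bound patients missing less often, planned MI gave 9.3 against a full-data 8.9. At 74 per arm with 50 imputations (800 trials, centre and week 42 left out), the 30% v 10% setting gave 9.15, 8.08, 8.07 and 9.18 in the same order. Missingness in that setting is 0.3 × 30% + 0.7 × 10% = 16% in the injection arm and 10% in the other, 13% overall, so the SAP's trigger is met.

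**The case against.** The strongest reply is that the bias needs a link the documents do not assert. Week 18 is the routine post-treatment clinic visit (Protocol 8.1), and a patient whose injection failed has reason to attend it. Non-attenders are chased, sent the booklet and, as a last resort, telephoned for the ODQ alone. This stands. Both the existence and the direction of the bias are open, and without a link the treatment difference is unbiased even though individual imputed values are wrong.

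Four stronger readings are tempting and should be resisted.

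- A reader might infer that failed injections are imputed as near-successes. They are placed near or somewhat above the arm average, and above patients who had no later surgery.
- A reader might infer that the imputation always repeats the complete-case bias. Where missingness depends on the week-18 ODQ itself, it removes about a quarter to two fifths.
- A reader might take the pilot criterion, "Fewer than 50% of patients in the injection group proceed to surgery", as an expected rate of later surgery. It is a progression rule with no timing. Surgery before week 18 does not cause this problem, because the week-18 score is then itself post-operative.
- A reader might call the imputation the only safeguard. Protocol 9.6 also plans a blinded review of whether reasons for missing data are informative, although SAP 18 does not repeat it.

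It can also be said that the SAP's list does not forbid further auxiliary variables. That is true, but none is named, and choosing one after seeing the data is weaker than naming it now. The effect is also small: the 30% v 10% setting concerns about 74 × 0.3 × 0.3 = 7 patients.

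**Conclusion.** The concern holds in conditional form. The named model uses possibly post-operative scores to impute a pre-operative one with no term for the operation, so surgery-bound injection patients are imputed too low at week 18. If a missing week 18 is associated with later surgery, planned multiple imputation has about the same bias as the complete-case analysis and cannot serve as a check on it. Under the assumed rates the size is roughly 0 to 1.5 points, about 14% of the 10-point target at the grid's largest value (1.4) and under half a standard error (1.4/3.03 = 0.46). A harsher assumption, 40% v 8% missing, gave 7.2 against 9.05, a bias of 1.85.

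The sign follows the direction of the association: towards injection if surgery-bound patients miss week 18 more often, towards surgery if less often. The documents give no later-surgery rate, timing or missingness pattern, so every size here rests on assumption. The gap in the model itself does not.

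**What to change.** In SAP 18, add to the imputation model, as an auxiliary variable, a dated indicator for microdiscectomy received after the week-18 time point and before the later ODQ, taken from Form 8. Leave the analysis model in SAP 17.4.1.2 unchanged.

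Keep the indicator separate from repeat TFESI. Protocol 7.2 links repeat injections to a favourable but partial response, which describes a different patient from one going on to surgery. In a run with an assumed share of repeat injections, one pooled indicator left most of the bias (8.2 against 8.9).

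The cost is one SAP sentence and one more imputation parameter. In the 74-per-arm runs the standard error was essentially unchanged (2.73 to 2.79). With no link between missingness and surgery, the indicator still reduced the root mean square error against full data from 0.77 to 0.65.

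There are three limits. Form 8 is not scheduled at weeks 30 or 42, so the indicator may be incomplete for patients without a week-54 or unscheduled visit, and its completeness should be reported. If missingness depends on baseline ODQ alone, the indicator can move the estimate by up to about 0.2 points. It does not remove bias from missingness that depends on the week-18 ODQ itself: 0.3 to 0.8 points remained in that scenario.

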## 19 Additional analyses

### Health economics

The trial health economist will prepare a full economics analysis plan.

### Additional analysis 1

As well as the model specified for our primary outcome analysis, we will also consider if any of the following baseline variables adjust our estimate of treatment effect by adding them to our mixed effects model as fixed effects:

- Age (Years)
- Sex (male/ female)
- BMI (KG /m^2)
- Duration of symptoms (weeks)

- Estimate volume of canal occupied by disc prolapse (Less than 25%, Between 25%-50%, Greater than 50%)

## 20 Safety Evaluations

### 20.1 Data sets analysed

For the safety analysis patients will be analysed according to which treatment was received in order to accurately represent the adverse effects of each treatment.

### 20.2 Presentation of the data

All adverse events (AEs) or adverse reactions (ARs) and serious adverse events (SAEs) reported by the clinical investigator will be presented in a table. The number (and percentage) of patients experiencing each AE/SAE will be presented for each treatment arm categorised by severity (mild, moderate, severe) within each SOC term and preferred term. For each patient, only the maximum severity experienced of each type of AE will be displayed. The number (and percentage) of patients experiencing each AE/SAE will be presented for each treatment arm categorised by causality (possibly, probably, almost certainly) within each SOC term and preferred term. For each patient, only the maximum relationship experienced of each type of AE will be displayed. Note that for relationship to TFESI is reported as 3 separate components (Injection, steroid, anaesthetic) and these will be reported separately. The number (and percentage) of occurrences of each AE/SAE will also be presented for each treatment arm. No formal statistical testing will be undertaken.

Adverse events will be categorised according to severity as “Mild”, “Moderate”, or “Severe”. They will also be classified in relation to the causality with the treatment as “Unrelated”, “Unlikely”, “Possibly”, “Probably”, or “Almost certainly”. Full details on the definition and classification of these adverse events are presented in section 10 of the protocol. For the purpose of EudraCT, ARs, fatal SAEs, non-fatal SARs and fatal SARs will be presented in separate tables.

## 21 Quality Control

To ensure quality control, an independent statistician will follow this SAP to independently program the primary analysis and safety data from the raw data. Any discrepancies found will be discussed with the senior trial statistician to resolve. No programming will be shared or shown between the statisticians. The independent statistician will also check the report against their output obtained from the statistical software.

